6.2 Venous Subjects

At Baseline, demographic information, medications and a medical history will be collected. Laboratory assessments, up to 14 days prior to the procedure will be recorded and include eGFR, serum creatinine (SCr), blood urea nitrogen (BUN), potassium (K), hemoglobin (Hgb), platelets (Plt), prothrombin time (PT), international normalized ratio (INR) and activated partial thromboplastin time (aPTT).

Duplex ultrasound examination will be collected at Baseline (up to 14 days prior to procedure), and 30 Days. Thrombus obstruction and location will be assessed by venous compressibility with incomplete compression indicating the presence of thrombus in that venous segment. Guidance from the imaging core laboratory will be provided for reference. Refer to the DUS core laboratory guidelines for detailed information. All DUS completed are requested to be transmitted to the core lab for analysis.

The pre-JETi venogram will be used to assess the initial degree of clot burden after catheter insertion into the venous system and prior to JETi Thrombectomy. The post-JETi Thrombectomy venogram will be used to assess removal after JETi Thrombectomy and prior to any adjunctive therapies used to treat underlying culprit lesions. The final venogram will be completed to assess clot removal after JETi Thrombectomy and any/all adjunctive therapies and prior to removal of the vascular sheath. All venograms will be transmitted to the core lab for review and adjudication.

The Villalta scale is a clinical severity score for the post-thrombotic syndrome (PTS).⁶ The Villalta PTS assessment rates the severity of 5 patient-reported symptoms (pain, cramps, heaviness, paresthesia, pruritus) and 6 clinician-observed signs (edema, skin induration, hyperpigmentation, pain during compression, venous ectasia, redness) of PTS on a 4-point scale (0 = none, 1 = mild, 2 = moderate, 3 = severe) for treated limb(s). The assessment will be collected at Baseline and at 30 days and is applicable to lower extremity DVT patients only.

Severity of leg pain assessed using a 7-point Likert scale (1 = no pain, 2 = very mild pain, 3 = mild pain, 4 = moderate pain, 5 = severe pain, 6 = very severe pain, 7 = extremely severe pain) will be collected at Baseline, Discharge, and 30 days. Note this assessment is applicable to lower extremity DVT patients only.

The Short Form (SF-12) is a self-reported outcome quality of life measure. Its completion is required at baseline, and 30 days. For post-procedurally consented subject, a baseline SF-12 will not be collected as the validity of this assessment is not supported when collected retrospectively.

Anticoagulants, antiplatelet, and thrombolytic medications will be collected for this Study at Baseline (medications that the patient was taking within the 30 days prior to admission and upon admission), Index Procedure, Discharge, and 30-day follow-up timepoint. Thrombolytics used during the index procedure will be collected.

AEs experienced by the patient during the procedure through discharge will be assessed by the physician to determine if related to any portion of the procedure. If the event has been determined to be

⁶ Lattimer CR, Kalodiki E, Azzam M, Geroulakos G. Validation of the Villalta scale in assessing post-thrombotic syndrome using clinical, duplex, and hemodynamic comparators. *J Vasc Surg Venous Lymphat Disord*. 2014;2(1):8-14.
doi:10.1016/j.jvsv.2013.06.003

related to the procedure, then a determination of relatedness to the JETi System is required. All events determined by the physician to be related to the JETi System will need to be assessed as to whether the event caused serious injury or death, and will be collected.

The schedule of events for venous subjects is located in **Section 6.2.6**.

Data collection at each timepoint is discussed in the sections below.

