6.2.1 Baseline

Subject preparation will occur in accordance with standard hospital policy for the care of interventional endovascular procedures. Note that no data will be recorded until consent is obtained.

The following data will be collected:

- Enrollment
- Demographics – including age, sex
- Medical history – subject medical history including general medical history, surgical history, vascular history, renal history, and thrombotic condition
- Medications: anticoagulant, antiplatelet, and thrombolytic medications (if applicable) taken within the 30 days prior to admission
- Laboratory assessments (within 14 days prior to the JETi procedure) such as:
 - eGFR
 - Serum Creatinine (SCr)
 - Blood urea nitrogen (BUN)
 - Potassium (K)
 - Hemoglobin (Hgb)
 - Platelets (Plt)
 - International normalized ratio (INR)
 - Prothrombin time (PT)
 - Activated partial thromboplastin time (aPTT)
- Clinical assessment – clinical assessment information including height, weight, blood pressure, heart rate, temperature, and respiratory rate
- Physical exam
- Villalta PTS assessment (at baseline or within 4 days prior to the index procedure)*; note this is applicable to lower extremity DVT subjects only.

** can be obtained via a non-study physician, including a referring physician; this will not be considered a protocol deviation*

- DUS (within 14 days prior to the index procedure)*

** can be obtained via a non-study physician, including a referring physician; this will not be considered a protocol deviation*

- Quality of life (QOL) questionnaire: SF-12 (not applicable for post-procedure consented subjects)

- Leg pain assessment by 7-point Likert Scale; note this is applicable to lower extremity DVT subjects only.

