6.2.6 Schedule of Events

The schedule of assessments for Venous Patients is listed in **Table 5**.

Table 6. Assessment Schedule for Venous Subjects

CIP Activity	Baseline	Index Procedure	Discharge	30 Days Follow-up (± 7 days) ¹	Unscheduled Visit
Enrollment ²	X				
Demographics	X				
Medical history	X				
Medications	X	X	X	X	X ³
Laboratory assessments					
eGFR	X ⁴				
Blood Urea Nitrogen (BUN)	X ⁴				
Serum Creatinine (Scr)	X ⁴				
Potassium (K)	X ⁴				
Hemoglobin (Hgb)	X ⁴				
Platelets	X ⁴				
International Normalized Ratio (INR)	X ⁴				
Prothrombin Time (PT)	X ⁴				
Activated Partial Thromboplastin Time (aPTT)	X ⁴				
Clinical assessment	X ⁴				
Physical assessment	X ⁴				
Villalta PTS assessment	X ⁵			X	
Leg pain assessment (7-point Likert scale)	X		X	X	
Imaging assessment					
Venogram		X ⁶			
Duplex ultrasound	X			X	
QOL (SF-12)	X ⁷			X	
Adverse event assessment/Device Deficiency assessment		X ⁸	X ⁸	X ⁸	X ⁸
Procedure, treatment information	X				

¹ In-office visit is required. A telephone contact or virtual visit is an option only for subject who would otherwise miss the visit due to being unable to complete an office visit

² retrospective consent is permitted

³ unscheduled Medications reported in Adverse Event form when applicable

⁴ assessment done within 14 days prior to procedure is acceptable

⁵ assessment done within 4 days prior to procedure is acceptable

⁶ includes pre-JETi, post-JETi, and final venograms

⁷ not applicable for post-procedure consented subjects

⁸ Serious adverse events (SAEs) and device deficiencies must be reported within 3 calendar days of Site becoming aware

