10.5 Deviations from CIP

The Investigator should not deviate from the CIP for any reason except in cases of medical emergencies when the deviation is necessary to protect the rights, safety, and well-being of the subject, or to eliminate an apparent immediate hazard to the subject. In that event, the Investigator will notify Sponsor immediately by phone or in writing.

All deviations will be collected, with the following exception:

- Baseline SF-12 in post-procedure consented subjects

The following deviations will be considered major:

- Late SAE, SADE, DD reporting
- Lack of patient informed consent
- Inclusion/exclusion criteria violations.

The Sponsor will not grant any waivers for CIP deviations. Sites must report all deviations to the Sponsor using the Deviation CRF. The Sponsor will monitor the occurrence of CIP for evaluation of investigator compliance to the CIP and regulatory requirements and handle according to written procedures. Investigators will inform their IRB/EC or equivalent committee of all CIP deviations in accordance with their specific IRB/EC or equivalent committee reporting policies and procedures.

In the event of repeated non-compliance, as determined by the Sponsor, a Sponsor's monitor or company representative will attempt to secure compliance by one or more of the following (and not limited to):

- Visiting the investigator and/or delegate
- Telephoning the investigator and/or delegate

- Corresponding with the investigator and/or delegate

Repeated non-compliance with the signed agreement, the CIP, or any other conditions of the study may result in further escalation in accordance with the Sponsor's written procedures, including securing compliance or, at its sole discretion, the Sponsor may terminate the investigator's participation in the study.

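### Baseline leg pain stays required from DVT subjects who consent after the procedure, although the plan drops their baseline SF-12 because retrospective collection is not valid

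*Combined protocol and SAP*

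**What the plan says.** Retrospective consent is allowed. Section 3.1 makes it conditional only on the assessments needed for the primary endpoints having been completed at baseline. Section 6.2.1 adds: "Note that no data will be recorded until consent is obtained".

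For these subjects the plan treats one instrument specially. Section 6.2 states that "a baseline SF-12 will not be collected as the validity of this assessment is not supported when collected retrospectively". Table 6 (section 6.2.6) marks the baseline SF-12 as "not applicable for post-procedure consented subjects". Section 10.5 collects all deviations with a single listed exception: "Baseline SF-12 in post-procedure consented subjects".

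Two other baseline measures with patient-reported content carry no such exemption:

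- **Leg pain.** Section 6.2.1 lists "Leg pain assessment by 7-point Likert Scale; note this is applicable to lower extremity DVT subjects only". The baseline cell in Table 6 has no footnote. Section 4.2.3 makes the score a descriptive endpoint at baseline, discharge and 30 days.
- **Villalta.** Section 6.2 says that it "rates the severity of 5 patient-reported symptoms (pain, cramps, heaviness, paresthesia, pruritus) and 6 clinician-observed signs". Section 6.2.1 lists "Villalta PTS assessment (at baseline or within 4 days prior to the index procedure" and lets a non-study or referring physician supply it without a deviation. The Table 6 footnote reads "assessment done within 4 days prior to procedure is acceptable".

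**The concern.** The reason given for dropping the SF-12 is that a self-report of the patient's state before treatment, given afterwards, is not a valid baseline. A leg pain rating is open to the same doubt: a patient asked after thrombectomy how much the leg hurt beforehand is answering in the light of the result. The plan does not say why the two scales are handled differently.

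At stake is how the leg pain summary reads. Scores recorded before treatment and scores recalled after it would be pooled in one baseline mean, and readers will set that mean against the discharge and 30-day means. With about 20 subjects in total, and only some of them with lower extremity DVT, a few recalled values could visibly move it. The deviation rule adds a smaller cost: a site that properly leaves the item blank has a deviation recorded for something it could not have done.

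**Working it through.** The plan gives no figure to reproduce here, so the check is a comparison of the text followed by an illustration of scale.

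**Step 1. Rules for a post-procedure consenter, by baseline measure.**

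| Rule | SF-12 | Leg pain | Villalta |
|---|---|---|---|
| Exempt at baseline (6.2, 6.2.1, Table 6) | Yes | No | No |
| Pre-procedure window | Not needed | None | 4 days |
| Outside physician as source | Not needed | None | Yes |
| Missing value excepted in 10.5 | Yes | No | No |
| Patient-reported content | All | All | 5 of 11 items |

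**Step 2. Can a pre-procedure value be counted on?** The condition on late consent covers only assessments for primary endpoints (3.1). Leg pain and Villalta are descriptive endpoints (4.2.3), so a subject can qualify with neither score on file. Because nothing is recorded for the study before consent, the value must come from an existing clinical record or be obtained afterwards.

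**Step 3. What happens without a record?** For leg pain two outcomes remain: a score given from memory, or a blank that counts as a deviation under 10.5. Section 11.3 lets a CRF worksheet serve as source for patient-reported outcomes, so a worksheet completed afterwards could pass as source-documented. Section 8.8 analyses available data and has no rule to flag or exclude such a score.

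**Step 4. Scale for leg pain (assumed inputs).** Let *f* be the share of DVT subjects with a recalled baseline and *e* the mean recall error (recalled minus true). The baseline mean shifts by *f* × *e*. The difference from discharge or from 30 days shifts by the same amount with opposite sign. The documents give neither input, so a range is used:

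- *f* = 10%, *e* = 0.5 point: 0.10 × 0.5 = 0.05
- *f* = 25%, *e* = 1 point: 0.25 × 1 = 0.25
- *f* = 50%, *e* = 1 point: 0.50 × 1 = 0.50
- *f* = 75%, *e* = 1 point: 0.75 × 1 = 0.75

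The shift in the mean is therefore about 0.05 to 0.75 point on a scale from 1 to 7.

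**Step 5. Scale for Villalta.** Items are scored 0 to 3. The five symptoms contribute 5 × 3 = 15 of 11 × 3 = 33 points, or 45%. With an assumed error of 0.25 to 0.5 point per symptom item and the same range of *f*, the mean total shifts by 5 × 0.25 × 0.10 = 0.125 to 5 × 0.5 × 0.75 = 1.875 points. Here *f* counts only subjects with no assessment in the 4-day window, so the upper end is less plausible than for leg pain.

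**The case against.** The strongest reply is that nothing tells sites to collect recalled scores. Section 11.4 bases data collection on source-documented chart review, section 8.8 simply excludes missing data, and the CRFs and core forms are under separate cover and may carry instructions. The bar on recording before consent limits study recording and does not mean that no clinical note exists. All of this stands. A reader might infer that the plan pushes sites towards recall; the documents do not support that. They leave the question open.

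Second, section 6.2 speaks only of the SF-12. A reader might infer that the plan concedes all retrospective self-reports to be invalid. It does not. Extending the reason to leg pain is an argument, though a close one, since both scales ask patients to rate their own state.

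Third, a reader might put Villalta on the same footing. That goes too far: it has a pre-procedure window and an outside source, and 6 of its 11 items are signs a clinician observes. What remains is that its five symptom items are exposed when no assessment in the window exists.

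Fourth, the deviation point is modest. A missing leg pain score is not among the major deviations in 10.5, and the plan makes other allowances, such as a missing baseline ABI in emergent limb ischemia (Table 5). None of them covers a missing leg pain or Villalta score.

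**Conclusion.** The inconsistency is in the text and is clearest for leg pain. The plan applies a validity rule to one self-reported baseline and leaves another required from the same subjects, with no window, source or exemption. Where no pre-procedure score was charted, the outcome is a recalled baseline or an unavoidable deviation.

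The shift of 0.05 to 0.75 point rests wholly on an assumed share of recalled baselines and an assumed recall error; neither its true size nor its direction can be derived from the documents. A reader might also infer that a defined change endpoint is biased. Section 4.2.3 lists scores by timepoint and section 4 rules out hypothesis testing, so what is affected is the descriptive before-and-after comparison. No primary endpoint and no test is touched, and only the lower extremity DVT subset of about 20 subjects is involved. This is a low-severity point that is worth correcting because the plan already contains the principle needed.

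**What to change.** 1. In sections 6.2 and 6.2.1 and in a new Table 6 footnote, state that for post-procedure consenters a baseline leg pain score is accepted only if it was documented before the procedure, and is otherwise left missing.
2. In the same places, state that the 4-day pre-procedure Villalta window applies to these subjects and that its symptom items are not to be scored retrospectively.
3. In section 10.5, add a missing baseline leg pain or Villalta score in post-procedure consenters to the deviation exception.

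The cost is a few lines of text and fewer baseline values among late consenters, which is the trade already accepted for the SF-12. Section 8.8 already covers the resulting missing values, so no new analysis method is needed.

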6.2.1 Baseline

Subject preparation will occur in accordance with standard hospital policy for the care of interventional endovascular procedures. Note that no data will be recorded until consent is obtained.

The following data will be collected:

- Enrollment
- Demographics – including age, sex
- Medical history – subject medical history including general medical history, surgical history, vascular history, renal history, and thrombotic condition
- Medications: anticoagulant, antiplatelet, and thrombolytic medications (if applicable) taken within the 30 days prior to admission
- Laboratory assessments (within 14 days prior to the JETi procedure) such as:
 - eGFR
 - Serum Creatinine (SCr)
 - Blood urea nitrogen (BUN)
 - Potassium (K)
 - Hemoglobin (Hgb)
 - Platelets (Plt)
 - International normalized ratio (INR)
 - Prothrombin time (PT)
 - Activated partial thromboplastin time (aPTT)
- Clinical assessment – clinical assessment information including height, weight, blood pressure, heart rate, temperature, and respiratory rate
- Physical exam
- Villalta PTS assessment (at baseline or within 4 days prior to the index procedure)*; note this is applicable to lower extremity DVT subjects only.

** can be obtained via a non-study physician, including a referring physician; this will not be considered a protocol deviation*

- DUS (within 14 days prior to the index procedure)*

** can be obtained via a non-study physician, including a referring physician; this will not be considered a protocol deviation*

- Quality of life (QOL) questionnaire: SF-12 (not applicable for post-procedure consented subjects)

- Leg pain assessment by 7-point Likert Scale; note this is applicable to lower extremity DVT subjects only.

6.2.2 Index Procedure

The thrombectomy procedure with the JETi System should be conducted in accordance with standard of care practice and approved labelling. All consented subjects who have the JETi Catheter introduced into the intended vasculature will be considered registered subjects and will be entered into the study.

The procedural data to be collected is described below:

- **Procedure information:** Start and end dates/times, amount of contrast used during the entire procedure, access sites, obstruction location, and the number of sessions within the procedure (If multiple sessions were needed, the location of the subject in between the sessions is requested).

- **Treatment information:** The treatments performed during the index procedure will be captured in the order of performance with specific details for each treatment. The treatment options will include the following:

- JETi mechanical thrombectomy (MT) only
- JETi in combination with one or more of the following treatments:
 - [REDACTED]
 - [REDACTED]

- **Imaging Assessments**

- Pre-JETi venogram: The pre-JETi venogram will be used to assess the initial degree of clot burden after catheter insertion into the vascular system and prior to JETi thrombectomy.
- Post-JETi venogram: The post-JETi thrombectomy venogram will be used to assess clot removal after JETi thrombectomy and prior to any adjunctive therapies used to treat underlying culprit lesions.
- Final venogram: The final venogram will be completed to assess the degree of clot removal after JETi thrombectomy and any/all adjunctive therapies and prior to removal of the vascular sheath.

All treated lower extremity venous vessels will be assessed using Marder score, per core laboratory assessment. Any other venous treated vessels (i.e., upper extremity) will be assessed by clot removal grade (per Section 4.1.1).

- **Acute success**, [REDACTED] core laboratory assessed:

- Device success: Thrombus removal grade II-III [REDACTED]

- Technical success: Thrombus removal grade II-III using [REDACTED] procedures (final), evaluated by [REDACTED]
- Procedural success: Technical success with no JETi-related MAEs within 5 days of registration or by discharge, whichever occurs first
- **Adverse Events and Device Deficiency assessment**
- **Medications:** Anticoagulant, antiplatelet, and thrombolytic medications administered during the procedure; anticoagulant and antiplatelet treatments within the peri-operative period should follow recommended societal guidelines.

6.2.3 Discharge

Discharge is defined as the subject leaving the treating or referral hospital. The following discharge data will be collected:

- Adverse events
- Medications: Anticoagulant, and antiplatelet medications
- Leg pain assessment by 7-point Likert Scale; note this is applicable to lower extremity DVT subjects only.

6.2.4 30-day Follow-up (Office Visit)

A 7-day window is required for the 30-Day visit (30 days \pm 7 days). The following data will be collected at the follow-up visit:

- Adverse events
- Medications: Anticoagulant, and antiplatelet medications
- Leg pain assessment by 7-point Likert Scale; note this is applicable to lower extremity DVT subjects only.
- DUS*
- Villalta PTS assessment*; note this is applicable to lower extremity DVT subjects only.
- QOL questionnaire: SF-12*

* can be obtained via a non-study physician, including a referring physician. This will not be considered a protocol deviation

6.2.5 Unscheduled Visit

Unscheduled visits may occur as clinically warranted, and data will be collected if the unscheduled visit is related to the JETi procedure and/or investigational device (as determined by the physician). Data on any imaging, clinical assessment, medication (anticoagulant, antiplatelet, and thrombolytic medications), AEs, DDs, and SAEs will be collected if applicable.

6.2.6 Schedule of Events

The schedule of assessments for Venous Patients is listed in **Table 5**.

Table 6. Assessment Schedule for Venous Subjects

CIP Activity	Baseline	Index Procedure	Discharge	30 Days Follow-up (± 7 days) ¹	Unscheduled Visit
Enrollment ²	X				
Demographics	X				
Medical history	X				
Medications	X	X	X	X	X ³
Laboratory assessments					
eGFR	X ⁴				
Blood Urea Nitrogen (BUN)	X ⁴				
Serum Creatinine (Scr)	X ⁴				
Potassium (K)	X ⁴				
Hemoglobin (Hgb)	X ⁴				
Platelets	X ⁴				
International Normalized Ratio (INR)	X ⁴				
Prothrombin Time (PT)	X ⁴				
Activated Partial Thromboplastin Time (aPTT)	X ⁴				
Clinical assessment	X ⁴				
Physical assessment	X ⁴				
Villalta PTS assessment	X ⁵			X	
Leg pain assessment (7-point Likert scale)	X		X	X	
Imaging assessment					
Venogram		X ⁶			
Duplex ultrasound	X			X	
QOL (SF-12)	X ⁷			X	
Adverse event assessment/Device Deficiency assessment		X ⁸	X ⁸	X ⁸	X ⁸
Procedure, treatment information	X				

¹ In-office visit is required. A telephone contact or virtual visit is an option only for subject who would otherwise miss the visit due to being unable to complete an office visit

² retrospective consent is permitted

³ unscheduled Medications reported in Adverse Event form when applicable

⁴ assessment done within 14 days prior to procedure is acceptable

⁵ assessment done within 4 days prior to procedure is acceptable

⁶ includes pre-JETi, post-JETi, and final venograms

⁷ not applicable for post-procedure consented subjects

⁸ Serious adverse events (SAEs) and device deficiencies must be reported within 3 calendar days of Site becoming aware

